8.2 Assessments During Treatment

Once the patient is confirmed to be eligible based on screening assessments, the following study assessments will be performed. See Table 8-1 and 8-2 for summary. One cycle is defined as 21 days. Day 1 visit procedures for any cycle of therapy are allowed a window of ± 3 days unless otherwise noted. Following the first cycle of therapy, patients may delay the start of a new cycle of therapy up to 2 weeks as necessary for personal activities, such as travel or vacation although every attempt should be made to keep patients on schedule. Treatment or visit delays due to public holidays, weather conditions, or natural disasters, do not constitute protocol violations.

The following treatment delays are allowable for patient coordination:

- Cycle 1, Day 8 – delay eribulin administration up to 3 days
- Cycle 2+, Day 1 – delay eribulin administration up to 14 days
- Cycle 2+, Day 8 – delay eribulin administration up to 3 days

8.2.1 Lead in Phase - Phase II only, Day -7/-6

- Blood for CSF1 and leukocyte phenotyping
 - For CSF1: 5 cc of blood will be drawn into a serum separator tube (gold top)
 - For leukocyte phenotyping: 10 cc of blood will be drawn into an EDTA tube (purple top)

- Tumor Biopsy Day 0/-1

8.2.2 During Cycle 1 (same for Phase Ib and Phase II except where noted below)

The following assessments will be performed prior to receiving treatment on Day 1:

- Medical history and physical examination
- Review of concomitant medications
- Laboratories, including complete blood count, chemistry panel and liver function tests.
- Blood for CSF1 and leukocyte phenotyping
- Blood for pharmacokinetics (Phase I only)

The following assessments will be performed after receiving treatment on Day 1 (Phase Ib only):

- Blood for pharmacokinetics will be drawn at 1 hour, 2 hours and 5 hours post treatment

The following assessment will take place on Day 2 (Phase Ib only):

- Blood for pharmacokinetics and CSF1 will be drawn 24 hours post Day 1 treatment

The following assessment will take place on Day 8:

- Medical history and symptom-driven physical examination
- Laboratories, including complete blood count with differential
- Review of concomitant medications

The following assessment will take place on Day 15:

- Liver function tests

8.2.3 During Subsequent Cycles (Cycle 2 and beyond)

The following assessments will be performed prior to receiving treatment on Day 1:

- Medical history and physical examination
- Review of concomitant medications
- Laboratories, including complete blood count, chemistry panel and liver function tests. Urine Pregnancy test will only be done for women of childbearing potential (Cycle 3+)
- Blood for CSF1 and leukocyte phenotyping (Cycle 2 and 4 Day 1 only)
- Blood for pharmacokinetics (Cycle 2, Phase Ib only)

The following assessments will be performed after receiving treatment on Day 1:

- Blood for pharmacokinetics will be drawn at 2 hours post treatment (C2, Phase Ib only)

The following assessments will take place on Day 8:

- Laboratories, including complete blood count with differential
- Review of concomitant medications

The following assessment will take place on Day 15:

- Liver function tests (Cycles 2 and 3 only)

Scans including all measurable and/or evaluable disease will be obtained every 6 weeks and at End of Treatment. Patients with either CR or PR and who have received at least 6 cycles of therapy may reduce the frequency of scans to every 9 weeks.

8.3 Follow-Up Assessments

Patients will be permitted to stay on treatment until they have disease progression.

Patients who develop progressive disease or Grade 3/4 toxicity that does not resolve after discontinuation of all study medications for 14 days will be removed from the study. All patients who leave the study must have a follow up visit within 30 days after their last dose of study medication. At this time, patients will have the following:

- Full medical history and physical exam for assessment of residual toxicities
- Blood draw for complete blood count with differential, chemistry panel, and liver function tests

If patients continue to have evidence of persistent toxicities at the first follow up visit, they will have continued monitoring at the discretion of the principal investigator until these symptoms are resolved or considered stable.

9.0 Criteria for Evaluation

9.1 Response Definitions

Evaluable for toxicity: All patients will be evaluable for toxicity from the time of their first treatment with PLX3397

Evaluable for objective response: Only those patients who have measurable disease present at baseline, have received at least one cycle of therapy, and have had their disease re-evaluated will be considered evaluable for response. These patients will have their response classified according to the definitions stated below. (Note: Patients who exhibit objective disease progression prior to the end of cycle 1 will also be considered evaluable.)

Evaluable Non-Target Disease Response: Patients who have lesions present at baseline that are evaluable but do not meet the definitions of measurable disease, have received at least one cycle of therapy, and have had their disease re-evaluated will be considered evaluable for non-target disease. The response assessment is based on the presence, absence, or unequivocal progression of the lesions.

Disease Parameters

Measurable disease: Measurable lesions are defined as those that can be accurately measured in at least one dimension (longest diameter to be recorded) as ≥ 20 mm (≥ 2 cm) by chest x-ray or as ≥ 10 mm (≥ 1 cm) with CT scan, MRI, or calipers by clinical exam. All tumor measurements must be recorded in millimeters (or decimal fractions of centimeters).

Malignant lymph nodes: To be considered pathologically enlarged and measurable, a lymph

node must be ≥ 15 mm (≥ 1.5 cm) in short axis when assessed by CT scan (CT scan slice thickness recommended to be no greater than 5 mm [0.5 cm]). At baseline and in follow-up, only the short axis will be measured and followed.

Non-measurable disease: All other lesions (or sites of disease), including small lesions (longest diameter < 10 mm [< 1 cm] or pathological lymph nodes with ≥ 10 to < 15 mm [≥ 1 to < 1.5 cm] short axis), are considered non-measurable disease. Bone lesions, leptomeningeal disease, ascites, pleural/pericardial effusions, lymphangitis cutis/pulmonitis, inflammatory breast disease, and abdominal masses (not followed by CT or MRI), are considered as non-measurable.

Note: Cystic lesions that meet the criteria for radiographically defined simple cysts should not be considered as malignant lesions (neither measurable nor non-measurable) since they are, by definition, simple cysts.

‘Cystic lesions’ thought to represent cystic metastases can be considered as measurable lesions, if they meet the definition of measurability described above. However, if non-cystic lesions are present in the same patient, these are preferred for selection as target lesions.

Target lesions: All measurable lesions up to a maximum of 2 lesions per organ and 5 lesions in total, representative of all involved organs, should be identified as *target lesions* and recorded and measured at baseline. Target lesions should be selected on the basis of their size (lesions with the longest diameter), be representative of all involved organs, but in addition should be those that lend themselves to reproducible repeated measurements. It may be the case that, on occasion, the largest lesion does not lend itself to reproducible measurement in which circumstance the next largest lesion which can be measured reproducibly should be selected. A sum of the diameters (longest for non-nodal lesions, short axis for nodal lesions) for all target lesions will be calculated and reported as the baseline sum diameters. If lymph nodes are to be included in the sum, then only the short axis is added into the sum. The baseline sum diameters will be used as reference to further characterize any objective tumor regression in the measurable dimension of the disease.

Non-target lesions: All other lesions (or sites of disease) including any measurable lesions over and above the 5 target lesions should be identified as **non-target lesions** and should also be recorded at baseline. Measurements of these lesions are not required, but the presence, absence, or in rare cases unequivocal progression of each should be noted throughout follow-up.

Methods for Evaluation of Measurable Disease

All measurements should be taken and recorded in metric notation using a ruler or calipers. All baseline evaluations should be performed as closely as possible to the beginning of treatment and never more than 4 weeks before the beginning of the treatment.

The same method of assessment and the same technique should be used to characterize each identified and reported lesion at baseline and during follow-up. Imaging-based evaluation is preferred to evaluation by clinical examination unless the lesion(s) being followed cannot be imaged but are assessable by clinical exam.

Clinical lesions: Clinical lesions will only be considered measurable when they are superficial

(e.g., skin nodules and palpable lymph nodes) and ≥ 10 mm (≥ 1 cm) diameter as assessed using calipers (e.g., skin nodules). In the case of skin lesions, documentation by color photography, including a ruler to estimate the size of the lesion, is recommended.

Chest x-ray: Lesions on chest x-ray are acceptable as measurable lesions when they are clearly defined and surrounded by aerated lung. However, CT is preferable.

Conventional CT and MRI: This guideline has defined measurability of lesions on CT scan based on the assumption that CT slice thickness is 5 mm (0.5 cm) or less. If CT scans have slice thickness greater than 5 mm (0.5 cm), the minimum size for a measurable lesion should be twice the slice thickness. MRI is also acceptable in certain situations (e.g. for body scans).

Use of MRI remains a complex issue. MRI has excellent contrast, spatial, and temporal resolution; however, there are many image acquisition variables involved in MRI, which greatly impact image quality, lesion conspicuity, and measurement. Furthermore, the availability of MRI is variable globally. As with CT, if an MRI is performed, the technical specifications of the scanning sequences used should be optimized for the evaluation of the type and site of disease. Furthermore, as with CT, the modality used at follow-up should be the same as was used at baseline and the lesions should be measured/assessed on the same pulse sequence. It is beyond the scope of the RECIST guidelines to prescribe specific MRI pulse sequence parameters for all scanners, body parts, and diseases. Ideally, the same type of scanner should be used and the image acquisition protocol should be followed as closely as possible to prior scans. Body scans should be performed with breath-hold scanning techniques, if possible.

PET-CT: At present, the low dose or attenuation correction CT portion of a combined PET-CT is not always of optimal diagnostic CT quality for use with RECIST measurements. However, if the site can document that the CT performed as part of a PET-CT is of identical diagnostic quality to a diagnostic CT (with IV and oral contrast), then the CT portion of the PET-CT can be used for RECIST measurements and can be used interchangeably with conventional CT in accurately measuring cancer lesions over time. Note, however, that the PET portion of the CT introduces additional data which may bias an investigator if it is not routinely or serially performed.

Tumor markers: Tumor markers alone cannot be used to assess response. If markers are initially above the upper normal limit, they must normalize for a patient to be considered in complete clinical response. Specific guidelines for both CA-125 response (in recurrent ovarian cancer) and PSA response (in recurrent prostate cancer) have been published [*JNCI* 96:487-488, 2004; *J Clin Oncol* 17, 3461-3467, 1999; *J Clin Oncol* 26:1148-1159, 2008]. In addition, the Gynecologic Cancer Intergroup has developed CA-125 progression criteria which are to be integrated with objective tumor assessment for use in first-line trials in ovarian cancer [*JNCI* 92:1534-1535, 2000].

Cytology, Histology: These techniques can be used to differentiate between partial responses (PR) and complete responses (CR) in rare cases (e.g., residual lesions in tumor types, such as germ cell tumors, where known residual benign tumors can remain).

during treatment when the measurable tumor has met criteria for response or stable disease is mandatory to differentiate between response or stable disease (an effusion may be a side effect of the treatment) and progressive disease.

Response Criteria

Evaluation of Target Lesions

Complete Response (CR): Disappearance of all target lesions. Any pathological lymph nodes (whether target or non-target) must have reduction in short axis to <10 mm (<1 cm).

Partial Response (PR): At least a 30% decrease in the sum of the diameters of target lesions, taking as reference the baseline sum diameters.

Progressive Disease (PD): At least a 20% increase in the sum of the diameters of target lesions, taking as reference the smallest sum on study (this includes the baseline sum if that is the smallest on study). In addition to the relative increase of 20%, the sum must also demonstrate an absolute increase of at least 5 mm (0.5 cm). (Note: the appearance of one or more new lesions is also considered progressions).

Stable Disease (SD): Neither sufficient shrinkage to qualify for PR nor sufficient increase to qualify for PD, taking as reference the smallest sum diameters while on study.

Evaluation of Non-Target Lesions

Complete Response (CR): Disappearance of all non-target lesions and normalization of tumor marker level. All lymph nodes must be non-pathological in size (<10 mm [<1 cm] short axis).

Note: If tumor markers are initially above the upper normal limit, they must normalize for a patient to be considered in complete clinical response.

Non-CR/Non-PD: Persistence of one or more non-target lesion(s) and/or maintenance of tumor marker level above the normal limits.

Progressive Disease (PD): Appearance of one or more new lesions and/or *unequivocal progression* of existing non-target lesions. *Unequivocal progression* should not normally trump target lesion status. It must be representative of overall disease status change, not a single lesion increase.

Although a clear progression of “non-target” lesions only is exceptional, the opinion of the treating physician should prevail in such circumstances, and the progression status should be confirmed at a later time by the review panel (or Principal Investigator).

Evaluation of Best Overall Response

The best overall response is the best response recorded from the start of the treatment until disease progression/recurrence (taking as reference for progressive disease the smallest measurements recorded since the treatment started). The patient's best response assignment will depend on the achievement of both measurement and confirmation criteria.

For Patients with Measurable Disease (i.e., Target Disease)

Target Lesions	Non-Target Lesions	New Lesions	Overall Response	Best Overall Response when Confirmation is Required*
CR	CR	No	CR	≥4 wks. Confirmation**
CR	Non-CR/Non-PD	No	PR	≥4 wks. Confirmation**
CR	Not evaluated	No	PR	
PR	Non-CR/Non-PD/not evaluated	No	PR	
SD	Non-CR/Non-PD/not evaluated	No	SD	Documented at least once ≥4 wks. from baseline**
PD	Any	Yes or No	PD	no prior SD, PR or CR
Any	PD***	Yes or No	PD	
Any	Any	Yes	PD	

* See RECIST 1.1 manuscript for further details on what is evidence of a new lesion. ** Only for non-randomized trials with response as primary endpoint. *** In exceptional circumstances, unequivocal progression in non-target lesions may be accepted as disease progression.
 
Note: Patients with a global deterioration of health status requiring discontinuation of treatment without objective evidence of disease progression at that time should be reported as “symptomatic deterioration.” Every effort should be made to document the objective progression even after discontinuation of treatment.
				

For Patients with Non-Measurable Disease (i.e., Non-Target Disease)

Non-Target Lesions	New Lesions	Overall Response
CR	No	CR
Non-CR/non-PD	No	Non-CR/non-PD*
Not all evaluated	No	not evaluated
Unequivocal PD	Yes or No	PD
Any	Yes	PD

* ‘Non-CR/non-PD’ is preferred over ‘stable disease’ for non-target disease since SD is increasingly used as an endpoint for assessment of efficacy in some trials so to assign this category when no lesions can be measured is not advised
		

Duration of Response

Duration of overall response: The duration of overall response is measured from the time measurement criteria are met for CR or PR (whichever is first recorded) until the first date that recurrent or progressive disease is objectively documented (taking as reference for progressive disease the smallest measurements recorded since the treatment started).

The duration of overall CR is measured from the time measurement criteria are first met for CR until the first date that progressive disease is objectively documented.

Duration of stable disease: Stable disease is measured from the start of the treatment until the criteria for progression are met, taking as reference the smallest measurements recorded since the treatment started, including the baseline measurements.

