2.2.2 Phase II

- To determine the response rate of PLX3397 in combination with eribulin in patients with chemotherapy pre-treated triple negative metastatic breast cancer.
- To determine the duration of response from the above therapy in this patient population.
- To determine the safety and tolerability of PLX3397 in combination with eribulin in this patient population.
- Correlative studies:
 - Correlation of CSF1 levels and response/duration of response to treatment.
 - Correlation of immune profiling in blood with PLX3397 treatment.
 - Correlate tumor immune profile before and after therapy with tumor subtype and response to therapy.

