3.2 Inclusion Criteria

- Pathologically confirmed diagnosis of breast cancer with documented progressive disease.
- Patients with stable brain metastases are eligible for this trial. Stable brain metastases defined as stable disease for one month and not on active treatment including steroids.
- Concomitant therapy with bisphosphonates is allowed.
- Stable dose coumadin anticoagulation is allowed, providing that anticoagulation can be safely held to an INR within normal range for the purpose of tumor biopsy. LMWH is the preferred method of anticoagulation.
- PT/INR and PTT \leq Grade 1 within two weeks before initial biopsy of visceral organs.
- Measurable disease, as defined by RECIST v1.1 guidelines or evaluable disease. Bone metastases must be evaluable.
- Disease amenable to core biopsy. Patients with pulmonary metastases as their only site of disease may enroll on this trial and will not undergo biopsy.
- For Phase Ib: patients with HER2 overexpressing disease must have been previously treated with trastuzumab (patients with HER2 overexpressing disease are not eligible for the Phase II trial).
- Age eighteen years or older.
- ECOG performance status ≤ 2 .
- Life expectancy of ≥ 12 weeks.
- Patients with \leq Grade 1 peripheral neuropathy are eligible for this trial using the CTCAE v4.0, regardless of use of therapy for neuropathy including gabapentin.
- Adequate bone marrow reserve: ANC ≥ 1000 , platelets $\geq 100,000$.
- Adequate renal function: serum creatinine $\leq 1.5x$ upper limit of normal OR calculated creatinine clearance ≥ 50 ml/min.
- Sodium and potassium levels \leq Grade 1.
- Adequate hepatic function: AST and ALT ≤ 2.5 x ULN, and total bilirubin $\leq 1.5x$ upper limit of normal. In patients with liver dysfunction due to hepatic metastases, AST and ALT are permitted to be ≤ 5 times the ULN. No clinical evidence of heart failure or history of untreated ejection fraction below the lower limit of normal per institutional standards, or significant QT prolongation ($>$ Grade 1, 480 msec) no history of congenital long QT syndrome, and no use of drugs known to increase the risk of Torsades de Point - patients may be eligible for study if the drug can be changed to another agent with less risk.
- Able to take oral medications and maintain hydration.

- Ability to give written informed consent and willingness to comply with the requirements of the protocol.

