For Phase II, sample size is based under the Simon's 2-stage optimal design for progression-free survival at 3 months as a single proportion. The study is designed to determine the following hypothesis with >80% power and 2-sided type I error of 5% using binomial approximation: H₀: PFS% <39% versus H_a: PFS% > 57% (with PLX3397), where PFS% is the proportion of progression-free (PFS) at 3 months. The PFS% of >57% would represent a clinically relevant improvement with the treatment in triple-negative patients with locally recurrent or metastatic breast cancer. Based on these considerations, a sample size of 51 evaluable patients is required for the study. We plan for a targeted enrollment of 56 patients with 10% dropout rate.

Interim assessment and stopping rules for Safety and efficacy

Safety and SAE data will be routinely monitored. Because of the possibility of unacceptable or excessive defined serious adverse events during treatment or the study enrollment period, stopping rules for safety/tolerability are also developed. We have set the maximum rate of treatment-related SAE at 15% in patient enrollment. Thus, we may consider terminating the study if the number of patients with SAE is greater than the number expected under the binomial distribution. The following table shows the early stopping guideline based on the number of SAE observed under the rate of unacceptable SAE in the group sequential enrolment for the study. For example, assuming the unacceptable rate of SAE is greater than 15%, if the study observes 3 or more SAE in the first 17 treated patients, then we may consider if the study should be stopped early.

Safety Stopping Rules:

Number of enrolled patients with excessive SAE to consider early study termination.

Number patients in study	1-17	18-29	30-41
Unacceptable SAE – 15%	3	4	6

Efficacy Stopping Rules

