12.2 Analysis Plan

Primary Efficacy Endpoint

Demographics and Baseline Characteristics

Demographic data (age, sex, race, ethnicity, body weight) and baseline disease characteristics will be tabulated and summarized and presented in data listings.

Progression Free Survival

Progression-free survival at 3 months (PFS) is defined as the proportion of patients alive and progression-free 90 days after Study Day 1. Duration of PFS is defined as the time from Study Day 1 to the earlier of disease progression or death due to any cause.

Progression free survival will be calculated from the first administration of PLX3397 with eribulin. The analyses of PFS will be performed using the Per Protocol population. These analyses are designed to include only objective progression events per the RECIST v1.1 criteria. Patients who do not have any post-baseline tumor assessments will be right censored on the date of Study Day 1. Patients who receive subsequent anti-cancer therapy before experiencing an event will be right censored at the date of the last tumor assessment prior to the date of initiation of subsequent therapy. Patients who have not experienced an event (and are not otherwise censored) at the time of data cutoff will be right censored on the date of their last tumor assessment

PFS will be estimated as a simple proportion based upon the results of the 12-week tumor assessment. Patients for whom this assessment is not performed will be included as failures, even if known to be alive at this timepoint. Confidence intervals will be provided. PFS and duration of PFS will also be estimated using Kaplan-Meier methods with associated confidence intervals.

Secondary and Supportive Efficacy Endpoints

Objective Response Rate

The objective response rate (ORR) is defined as the proportion of patients for whom the best overall response at the time of data cutoff is confirmed CR or confirmed PR as assessed per RECIST v 1.1 criteria. A table defining the derivation of best overall response to be applied will be provided in the SAP.

The analysis of ORR will employ the Per Protocol population. Patients who do not have any post-baseline tumor assessments will be counted as non-responders.

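### Sections 9.1 and 12.2 give inconsistent denominators for the objective response rate, and the Per Protocol population that 12.2 relies on is not defined

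*Combined protocol and SAP*

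**What the plan says.** Response rate is the first Phase II secondary objective in 2.2.2: "To determine the response rate of PLX3397 in combination with eribulin in patients with chemotherapy pre-treated triple negative metastatic breast cancer". Four places bear on who is in its denominator.

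- **Section 9.1** defines the response-evaluable set as "Only those patients who have measurable disease present at baseline, have received at least one cycle of therapy, and have had their disease re-evaluated". A note adds patients whose disease objectively progresses before cycle 1 ends. Patients with only non-measurable lesions go into a separate non-target category, and their response table has CR, non-CR/non-PD, not evaluated and PD, but no PR.
- **Section 12.2** states: "The analysis of ORR will employ the Per Protocol population". It continues: "Patients who do not have any post-baseline tumor assessments will be counted as non-responders". It sets no measurable-disease condition. The Per Protocol population is not defined anywhere in the document.
- **Section 3.2** admits "Measurable disease, as defined by RECIST v1.1 guidelines or evaluable disease", so patients without measurable disease can enrol.
- **Section 12.6** replaces Phase II patients who have no evaluation, or who have had only one eribulin dose or under 14 days of PLX3397, when the reason is something other than progression or toxicity. It does not say whether replaced patients leave the analysis.

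Nothing says whether 9.1 or 12.2 governs ORR.

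**The concern.** The two sections treat the same patient differently. Someone who starts treatment, stops for toxicity, clinical deterioration or death, and never has a re-evaluation falls outside the 9.1 set, but is a non-responder under 12.2 if the Per Protocol population includes her. Leaving such patients out pushes ORR upward, because none of them can be a responder.

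The second difference is measurability. Under 12.2 as written, an evaluable-only patient can sit in the denominator although the 9.1 table gives her no route to PR, only to CR. Including such patients tends to lower ORR; 9.1 excludes them.

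The study has a single arm, so ORR can be read only against outside figures. The eribulin-alone response rates quoted in 1.2 are 9.3%, 11.5% and 12.2%. A few percentage points from the choice of denominator could affect whether the combination appears to add activity. A rule left open at the design stage also has to be settled later, possibly with the data in view.

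**Working it through.** **Inputs from the plan.** Section 12.1 states "a sample size of 51 evaluable patients is required for the study" and "We plan for a targeted enrollment of 56 patients with 10% dropout rate". Section 12.2 specifies exact binomial 95% intervals (Clopper-Pearson used here).

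**Reproducing the plan's figure.** 51 × 1.10 = 56.1, which gives the stated 56. Dividing instead, 51 / 0.90 = 56.7, gives 57. The stated 56 is reproduced to within one patient. The plan states no expected ORR, no ORR denominator and no ORR precision, so there is nothing further to reproduce.

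**Assumptions.**

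- 7 responders, held the same under both rules. This is near the quoted eribulin-alone rates: 56 × 12.2% = 6.8.
- 12.2 denominator of 56. This is an upper bound at planned enrolment, since an undefined Per Protocol set could be smaller.
- 9.1 denominator starting at 51, taking the 56 − 51 = 5 allowed-for dropouts as patients never re-evaluated.
- Share of re-evaluated patients with non-measurable disease: 0% to 30%. The documents give no figure.

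**Formula.** ORR = responders / denominator. The 9.1 denominator is 51 × (1 − non-measurable share), rounded: 51 × 0.9 = 45.9, so 46; 51 × 0.8 = 40.8, so 41; 51 × 0.7 = 35.7, so 36.

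| Rule | ORR | 95% CI | Gap to 12.2 (points) | Ratio to 12.2 |
|---|---|---|---|---|
| 12.2, upper bound | 7/56 = 12.5% | 5.2–24.1 | – | – |
| 9.1, all measurable | 7/51 = 13.7% | 5.7–26.3 | 1.2 | 56/51 = 1.10 |
| 9.1, 10% non-measurable | 7/46 = 15.2% | 6.3–28.9 | 2.7 | 56/46 = 1.22 |
| 9.1, 20% non-measurable | 7/41 = 17.1% | 7.2–32.1 | 4.6 | 56/41 = 1.37 |
| 9.1, 30% non-measurable | 7/36 = 19.4% | 8.2–36.0 | 6.9 | 56/36 = 1.56 |

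The ratio does not depend on the number of responders, but the gap in points does. Over the same four 9.1 cases it is 1.1 to 6.0 points with 6 responders (12.2 rate 10.7%) and 1.8 to 9.9 points with 10 (12.2 rate 17.9%). If every patient has measurable disease, completes a cycle and is re-evaluated, both denominators are 56 and the gap is zero.

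**Could the Per Protocol label reconcile the sections?** If it meant the 9.1 set, every member would already have been re-evaluated or have progressed objectively. The 12.2 sentence on patients without assessments would then have almost nothing to act on. That sentence makes sense only if the 12.2 population is wider than the 9.1 set.

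**The case against.** The best defence is that 12.2 governs. It defines ORR, names its population and gives its missing-data rule. Section 9.1 sits among the evaluation criteria, says whose response is classified, and never mentions ORR or a denominator. That is a reasonable reading, but the plan does not state it. It would still leave the Per Protocol population undefined and the measurability question open.

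Several stronger readings are tempting and are not supported:

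- *That 9.1 removes early failures in general.* Its note keeps objective progressors before the end of cycle 1. What it loses is narrower: patients never re-evaluated, and those stopping within cycle 1 without objective progression.
- *That 12.2 uses all 56 patients.* It uses an undefined Per Protocol set, and one requiring minimum exposure could bring the two rules close together.
- *That unassessed patients always create a gap.* Section 12.6 replaces some of them, though not those who stop for progression or toxicity, where the two rules still differ.
- *That the rates must differ materially.* On the plan's own 56 and 51 the difference is 1.2 points with wide, overlapping intervals. Larger gaps need an assumed share of non-measurable disease.
- *That the choice will be made after seeing results.* The text leaves room for this; nothing shows an intention.

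Holding responders fixed is also a simplification. A non-measurable patient can reach CR, which may count under 12.2 but not 9.1. Section 12.2 requires confirmed responses, while the 9.1 table footnote limits confirmation to non-randomised trials with response as the primary endpoint.

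Finally, ORR is secondary and carries no hypothesis test or stopping threshold. That limits the stakes but does not remove the inconsistency.

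**Conclusion.** The inconsistency is in the current text. It is direct for treated patients with no post-baseline assessment. For evaluable-only patients it follows from 12.2's silence on measurability combined with 3.2.

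Confidence is high on the wording and low on the size. The 9.1 rate exceeds the 12.2 rate by a factor of 1.10 using only the plan's 56 and 51, and by 1.22 to 1.56 if 10% to 30% of re-evaluated patients have non-measurable disease. These ratios assume the same responders under both rules, a 12.2 denominator at its upper bound of 56, and five patients never re-evaluated.

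Only the secondary ORR is affected. The two-stage PFS decision rule does not use this denominator. The point should be fixed, but it does not threaten the primary analysis.

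**What to change.** State one ORR denominator in both sections:

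1. The main ORR population is all treated Phase II patients with measurable disease at baseline. Those without a post-baseline assessment count as non-responders.
2. In 12.2, replace the undefined Per Protocol population with this set for ORR.
3. In 9.1, drop the one-cycle and re-evaluation conditions for the main ORR. Keep the present 9.1 set only as a labelled sensitivity analysis.
4. Report patients with only non-measurable disease separately, as CR, non-CR/non-PD or PD.

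This keeps the conservative missing-data rule of 12.2 and the measurability condition of 9.1. The cost is wording in two sections, with no change to sample size, data collection or patient management. The one downside is that ORR may come out lower than under 9.1.
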